**The Intended duration of treatment with axitinib (weeks) =**

$$(\text{last dose date of axitinib} - \text{first dose date of axitinib} + 1) / 7$$

**Duration of exposure to axitinib (weeks) =**

$$(\text{last dose date of axitinib} - \text{first dose date of axitinib} + 1) / 7$$

**Cumulative dose** is the sum of the actual doses of axitinib received in the study.

**Actual Dose Intensity (DI)**

- Overall actual DI (mg/week) = [overall cumulative dose (mg)] / [intended treatment duration (weeks)]

### Relative Dose Intensity (RDI)

- $RDI (\%) = 100 \times [\text{overall cumulative dose}] / [\text{intended cumulative dose per week} \times \text{number of weeks from first dose of study drug to last dose of axitinib}]$
- $= 100 \times [\text{overall cumulative dose}] / [7 \times 2 \times d \times \text{duration of exposure to axitinib (weeks)}]$ , where  $d = 3$  or  $5$ .

#### 6.5.3.3. Dose Reductions

Applicable to avelumab. Dose reduction is defined as actual non-zero dose < 90% of the planned dose.

Applicable to axitinib. Dose reduction is defined as a change to a non-zero dose level lower than that planned in the protocol.

The number and percentage of patients with at least one dose reduction as well as a breakdown of dose reductions (1, 2, 3,  $\geq 4$ ) will be summarized.

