5.3.5.1. Inpatient Axitinib Dose Escalation and Dose Reduction

In the Dose Finding Phase, inpatient axitinib dose escalation is not permitted for patients treated at DL-1A.

Inpatient axitinib dose escalation is permitted for patients treated in the Dose Finding Phase at DL-1B (avelumab 10 mg/kg Q2W + axitinib 3 mg BID). In these patients, after the completion of the primary DLT observation period (4 weeks), inpatient axitinib dose escalation to 5 mg BID may occur according to the criteria reported below.

In the Dose Expansion Phase, inpatient axitinib dose escalation up to 10 mg BID may occur according to the criteria reported below.

Criteria for Inpatient Dose Escalation: Patients who tolerate the current axitinib dose without Grade >2 drug-related adverse events for 2 consecutive weeks (in the Dose Expansion Phase) or 4 consecutive weeks (in the Dose Finding Phase, only DL-1B), and who do not experience BP >150/90 mm Hg or concurrent administration of antihypertensive medication, have the option to have their axitinib dose increased (by one dose level at a time [Table 4]). Patients treated in the Dose Finding Phase at DL-1B have the option to have their axitinib dose increased to a maximum dose of 5 mg BID. Particular attention should be provided to a patient's overall safety profile prior to implementing inpatient axitinib dose escalation.

Table 4. Axitinib Dose Levels

Dose Level	Dose
+2	10 mg BID
+1	7 mg BID
Starting Dose	5 mg BID
-1	3 mg BID
-2	2 mg BID

Patients will be monitored closely for toxicity, and axitinib treatment may be adjusted by dosing interruption with or without dose reduction as indicated in Table 4. Dosing interruption and/or dose reduction by 1, and if needed, up to 2 dose levels (one dose level reduction at a time) will be allowed depending on the type and severity of toxicity encountered. Management of patients requiring more than 2 dose reductions should be discussed with the sponsor's medical monitor.

Patients who have undergone dose reduction may also undergo dose re-escalation back to the previous dose level at the discretion of the Investigator in the absence of Grade \geq 2 non-hematologic treatment-related toxicity for at least 28 days.

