### 3.4. Baseline Variables

#### 3.4.1. Study drug, study treatment and baseline definitions

In this study ‘**study drug**’ refers to avelumab or axitinib and ‘**study treatment**’ (or ‘**treatment group**’) refers to one of the following:

- DL1 with lead-in: axitinib 5 mg oral BID followed by avelumab 10 mg/kg IV Q2W in combination with axitinib 5 mg oral BID, or
- DL-1A with lead-in: axitinib 5 mg oral BID followed by avelumab 5 mg/kg IV Q2W in combination with axitinib 5 mg oral BID, or
- DL-1B with lead-in: axitinib 3 mg oral BID followed by avelumab 10 mg/kg IV Q2W in combination with axitinib 3 mg oral BID, or

- DL1: avelumab 10 mg/kg IV Q2W in combination with axitinib 5 mg oral BID, or
- DL-1A: avelumab 5 mg/kg IV Q2W in combination with axitinib 5 mg oral BID, or
- DL-1B: avelumab 10 mg/kg IV Q2W in combination with axitinib 3 mg oral BID.

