## 6. ANALYSES AND SUMMARIES

Refer to Section 4 for definitions of analysis sets and Section 5.2 for general methodology.

At the time of the SAP amendment 01 (SAP V2), the dose-finding phase had been completed and the only dose levels tested in the study will be DL1 and DL1 with lead-in. Therefore, no randomization will be implemented in the study.

Data will be summarized separately for DL1 and for DL1 with lead-in as well as for both treatment groups combined.

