#### **6.5.3. Study treatment compliance and exposure**

The following analyses will be based on the safety analysis set by treatment group.

Cycle definitions for study drugs that are administered in combination apply to all the study drugs in the combination. Ie, cycle is patient-dependent, rather than study-drug-dependent when study drugs are administered in combination.

For Cycle X, actual cycle start date for each patient is

- the earliest start date of dosing in the Cycle X day 1 visit eCRF exposure page, if the patient received study treatment on that visit (ie, any study drug with dose>0 at that visit)
- the first day of assessments in the Cycle X day 1 visit, if the patient did not receive study treatment on that visit (ie, all study drugs had dose=0 at that visit). Use start date in the exposure page if available; if start date is not available then use date of collection of vital signs on Cycle X day 1 visit.

Actual cycle end date for each patient is,

- for all cycles X except the last cycle, actual cycle end date = actual cycle (X+1) start date – 1 day;
- for the last cycle, actual cycle end date = actual cycle start date + 14 days – 1 day

**Cycle duration** (weeks) = (actual cycle end date – actual cycle start date + 1)/7

When summarizing exposure for each study drug, only cycles from first dose of study treatment until the last cycle with non-zero dose of at least one of the study drugs should be included.

Exposure will be summarized (per cycle and/or overall) as dose received (cumulative dose, actual dose intensity) and as dose received relative to intended dose (relative dose intensity [RDI]).

The derivations below are provided for the following:

- Avelumab administered as a 1-hour IV infusion at a dose of 10 mg/kg or 5 mg/kg once every 2 weeks in 2-week cycles.
- Axitinib administered BID PO at a dose of 5 mg or 3 mg.

Analysis of exposure will be based on the calculated actual dose levels

- Avelumab - total dose / weight
- Axitinib – total dose.

Exposure and compliance will be summarized by cycle (avelumab only) and overall (avelumab and axitinib) for each study drug in each treatment group.

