#### 6.5.3.4. Dose escalations

Applicable to axitinib only.

Dose escalation is defined as a change to a dose level higher than that planned in the protocol.

The number and percentage of patients with at least one dose escalation as well as a breakdown of dose escalations (1, 2,  $\geq 3$ ) will be summarized.

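### Axitinib dose reductions and escalations are counted against the planned 5 mg BID dose, not the previous dose, so four of the eight one-step moves on the protocol's dose ladder are misclassified in the exposure tables

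*SAP*

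**What the plan says.** For axitinib, SAP 6.5.3.3 states: "Dose reduction is defined as a change to a non-zero dose level lower than that planned in the protocol". SAP 6.5.3.4 states: "Dose escalation is defined as a change to a dose level higher than that planned in the protocol". Each section then tabulates how many patients had any such change, with a breakdown by number of changes (1, 2, 3 and 4 or more for reductions; 1, 2 and 3 or more for escalations).

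The reference dose is fixed. SAP 6.5.3 gives it as "Axitinib administered BID PO at a dose of 5 mg or 3 mg", and SAP section 6 records that "the only dose levels tested in the study will be DL1 and DL1 with lead-in". SAP 3.4.1 defines that level as "DL1: avelumab 10 mg/kg IV Q2W in combination with axitinib 5 mg oral BID". The planned axitinib dose is therefore 5 mg BID for everyone.

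Protocol 5.3.5.1 (Table 4) sets the ladder 2, 3, 5, 7 and 10 mg BID. It says "In the Dose Expansion Phase, inpatient axitinib dose escalation up to 10 mg BID may occur according to the criteria reported below". Its limit on reductions reads: "up to 2 dose levels (one dose level reduction at a time) will be allowed depending on the type and severity of toxicity encountered". It adds: "Patients who have undergone dose reduction may also undergo dose re-escalation back to the previous dose level".

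**The concern.** In the protocol a reduction is a step down from the current level. Table 5 repeatedly tells the investigator to go down one level from wherever the patient is. The SAP asks a different question: is the new level below or above 5 mg? The two agree while a patient is moving away from 5 mg and disagree when the patient is moving back towards it.

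At stake is the accuracy of the axitinib reduction and escalation counts. Dose Expansion patients can be escalated above 5 mg and then cut back. In those patients a dose cut is either not counted or appears as a further escalation.

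**Working it through.** The documents give no figure to reproduce. The check applies the SAP wording literally to the protocol's ladder.

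**Inputs.** Planned dose 5 mg BID (SAP 3.4.1, 6 and 6.5.3). Levels 2, 3, 5, 7 and 10 mg BID, with one-level steps in both directions (Protocol 5.3.5.1).

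**SAP rule.** For a change to new level *b*: reduction if 0 < *b* < 5; escalation if *b* > 5; neither if *b* = 5.

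**Comparison rule.** For a change from *a* to *b*: reduction if 0 < *b* < *a*; escalation (or re-escalation) if *b* > *a*.

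The eight one-step moves:

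| Move (mg BID) | SAP rule | Against previous dose | Agree? |
|---|---|---|---|
| 5 to 7 | escalation | escalation | yes |
| 7 to 10 | escalation | escalation | yes |
| 10 to 7 | escalation | reduction | no |
| 7 to 5 | neither | reduction | no |
| 5 to 3 | reduction | reduction | yes |
| 3 to 2 | reduction | reduction | yes |
| 2 to 3 | reduction | re-escalation | no |
| 3 to 5 | neither | re-escalation | no |

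Four of eight disagree.

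The effect on a patient's counts depends on the path:

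| Path (mg BID) | SAP rule | Against previous dose |
|---|---|---|
| 5-7-5 | 1 escalation, 0 reductions, 1 uncounted | 1 escalation, 1 reduction |
| 5-7-10-7 | 3 escalations, 0 reductions | 2 escalations, 1 reduction |
| 5-7-10-7-5 | 3 escalations, 0 reductions, 1 uncounted | 2 escalations, 2 reductions |
| 5-3-2-3 | 3 reductions, 0 escalations | 2 reductions, 1 re-escalation |
| 5-3-2-3-5 | 3 reductions, 0 escalations, 1 uncounted | 2 reductions, 2 re-escalations |

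Three consequences follow.

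1. On the first three paths the patient had at least one cut but is absent from the patients with any reduction. This is the one error that reaches a headline percentage. It needs an earlier rise above 5 mg. Protocol 3.1 bars such escalation in dose finding except at DL-1B, which was not used, so it can arise only in Dose Expansion.
2. A patient who comes down to 2 mg stepwise already has two reductions counted (5 to 3, 3 to 2). The later 2 to 3 step makes three. It moves the patient within the reduction breakdown and leaves the any-reduction count alone.
3. A patient who climbs to 10 mg stepwise already has two escalations counted (5 to 7, 7 to 10). The later 10 to 7 cut makes three. It moves the patient from 2 to the 3-or-more category and leaves the any-escalation count alone.

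**Cross-check with the adverse-event tables.** SAP 6.6.1 identifies events leading to dose reduction from the eCRF action-taken field, and SAP 6.6.1.1 and 6.6.1.2 tabulate them for axitinib. They do not use the 6.5.3.3 definition. A 10 to 7 cut recorded there as a reduction would appear as a reduction in those tables and as an escalation in the exposure tables.

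**The case against.** The strongest defence is that the planned dose is a legitimate reference. It shows whether a patient fell below or rose above the intended dose, and it matches the rest of the exposure section: avelumab reductions are judged against 90% of the planned dose, and axitinib relative dose intensity uses 3 or 5 mg. Replacing it outright would mix returns to the 5 mg starting dose with cuts below it. That part stands, and the comparison with the planned dose should be kept. It does not rescue the present rule, because counting changes as 1, 2, 3 and so on does not measure being below plan: a recovery from 2 to 3 mg adds one.

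Another defence is to read the planned dose as the patient's current prescribed dose. SAP 6.5.3 and the dose-intensity formula in 6.5.3.2 fix it at 5 or 3 mg, so that reading is not available.

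A reader might also infer more than the documents support:

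- *That the reduction count is a main criterion for the RP2D.* Protocol 3.4 draws attention to discontinuation for treatment-related adverse events, and Protocol 3.1.1.2 refers to safety only in general terms. Neither names dose-reduction counts, and SAP 5.1.2 attaches no decision rule to Dose Expansion.
- *That toxicity-driven cuts vanish from the report.* Those recorded as dose reductions in the action field still reach the adverse-event tables.
- *That a direct drop from 10 to 5 mg is a further example.* The protocol provides for toxicity reductions one level at a time, so 10 to 7 and 7 to 5 are the relevant steps.
- *That every recovery inflates the reduction count.* Only 2 to 3 does; 3 to 5 adds nothing.

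**Conclusion.** The point holds as a counting error in the descriptive axitinib exposure tables. Four of the eight one-step moves are misclassified. The headline effect is that Dose Expansion patients whose only cuts come after an escalation and stop at 5 mg or above are left out of the any-reduction count. The other effects are shifts within the two breakdowns, recoveries to 5 mg that are not counted, and a possible contradiction with the adverse-event tables.

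DLTs, efficacy endpoints and relative dose intensity do not use these definitions and are unaffected.

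The conclusion assumes that the SAP sentences are programmed as written and that doses move one level at a time. The documents do not say how often these sequences occur, so the number of patients affected cannot be estimated. The correction is worthwhile because the written rule gives the wrong direction for moves the protocol expressly allows.

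**What to change.** Reword the axitinib definitions in SAP 6.5.3.3 and 6.5.3.4:

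- a reduction is a change to a non-zero level lower than the last non-zero prescribed level;
- an escalation is a change to a level higher than the last non-zero prescribed level, with re-escalations after a reduction tabulated separately.

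Keep the comparison with the planned dose as two rows of its own: patients ever below, and patients ever above, the planned dose.

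Referring to the last non-zero level also settles a case the present wording leaves open. Resuming at the same level after an interruption, for example 3 mg, then 0, then 3 mg, would be neither a reduction nor an escalation.

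The cost is two SAP sentences, one derivation and two table rows. The dose records are already needed for cumulative dose and interruptions. No new data are needed and no patient's treatment changes.

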#### 6.5.3.4. Dose escalations

Applicable to axitinib only.

Dose escalation is defined as a change to a dose level higher than that planned in the protocol.

The number and percentage of patients with at least one dose escalation as well as a breakdown of dose escalations (1, 2,  $\geq 3$ ) will be summarized.

#### 6.5.3.5. Dose interruptions

Applicable to axitinib only.

An interruption is defined a 0 mg dose administered on one or more days. What follows defines how dose interruptions will be counted in the case of multiple dose interruptions.

- If an interruption occurs consecutively for at least two days due to the same reason, then it will be counted only once (example: If the actual dose on days 1-3 is 10 mg and actual dose on days 4-5 is 0 mg and dose interruption on days 4-5 is due to AE, then the total number of dose interruptions is 1).
- If an interruption occurs consecutively for at least two days due to different reasons, then it will be counted for each reason (example: If the actual dose on days 1-3 is 10 mg and actual dose on days 4-5 is 0 mg and dose interruption on day 4 is due to AE and dose interruption on day 5 is due to dosing error, then the total number of dose interruptions is 2).
- If an interruption occurs for more than one day due to the same reason, but the days are not consecutive, ie there is at least one dosing day in between, then each dose interruption will be counted as a different occurrence (example: If the actual dose on days 1, 3 and 5, is 10 mg and actual dose on days 2 and 4 is 0 mg, and dose interruptions on day 2 and 4 are both due to dosing error, the total number of dose interruptions is 2).

A dose interruption is not considered a dose reduction.

The number and percentage of patients with dose interruptions and the corresponding reasons will be summarized.

#### **6.5.3.6. Dose Delays**

Applicable to avelumab only.

Dose delay is the difference between the actual time between two consecutive non-zero doses and the planned time between the same two consecutive non-zero doses.

In Cycle 1,

$$\text{Dose Delay (days)} = \text{day of first dose of avelumab} - 1.$$

In Cycle >1

$$\text{Dose Delay (days)} = \text{Date of first dose of avelumab in Cycle } x - \text{Date of first dose of avelumab in Cycle } (x-1) - 14.$$

Dose Delays will be grouped into the following:

- No delay
- 1-3 days delay
- 4-6 days delay
- 7 or more days delay

For example, for avelumab, administered on a 2-week schedule, if one patient receives avelumab on Day 1, then the next avelumab administration date will be on Day 15; however, if the patient receives avelumab at Day 16, 17 or 18, this is considered as 1-3 days delay.

No delay and 1-3 days delay will also be summarized together.

The number and percentage of patients with delayed study drug administration and maximum length of delay, ie, the worst case of delay if patients have multiple dose delays will be summarized.

#### **6.5.3.7. Infusion rate reductions**

Applicable to avelumab only.

The number and percentage of patients with at least one infusion rate reduction of  $\geq 50\%$  compared to the first infusion rate reported in the eCRF as well as the frequency of patients with 1, 2, 3 or  $\geq 4$  infusion rate reductions of  $\geq 50\%$  will be summarized.

#### 6.5.3.8. Infusion interruptions

Applicable to avelumab only.

An infusion interruption is defined as an infusion that is stopped and re-started on the same day (ie, for a visit more than one infusion start time and infusion end time are recorded).

The number and percentage of patients with at least one infusion interruption as well as the frequency of patients with 1, 2, 3, or  $\geq 4$  infusion interruptions will be summarized.

#### 6.5.4. Concomitant medications and non-drug treatments

The following analyses will be based on the safety analysis set by treatment group.

**Concomitant medications** are medications, other than study medications, which started prior to first dose date of study treatment and continued on on-treatment period as well as those started during the on-treatment period. **Prior medications** are medications, other than study medications and pre-medications for study drug, which are started before the first dose of study treatment.

Prior and concomitant medications will be summarized from the 'General Concomitant Medications' eCRF page. Pre-medications for study drug will also be summarized separately from the 'Pre-Medication Treatment' eCRF page.

Summary of prior medications, summary of concomitant medications and summary of pre-medications will include the number and percentage of patients by Anatomical Therapeutic Chemical (ATC) Classification level 2 and preferred term. A patient will be counted only once within a given drug class and within a given drug name, even if he/she received the same medication at different times. If any prior or concomitant medication is classified into multiple ATC classes, the medication will be summarized separately under each of these ATC classes. The summary tables will be sorted on decreasing frequency of drug class and decreasing frequency of drug name in a given drug class. In case of equal frequency regarding drug class (respectively drug name), alphabetical order will be used. In case any specific medication does not have ATC classification level 2 coded term, it will be summarized under 'Unavailable ATC classification' category.

A listing of prior medications and a listing of concomitant medications will be created with the relevant information collected on the 'General Concomitant Medications' eCRF page. A listing of pre-medications will be created with the relevant information collected on the 'Pre-Medication Treatment' eCRF page.

All concurrent procedures, which were undertaken any time during the on-treatment period, will be listed according to the eCRF page 'General Non-drug Treatments'.

A listing of concurrent procedures will be created with the relevant information collected on the 'General Non-drug Treatments' eCRF page.

### 6.5.5. Subsequent anti-cancer therapies

The following analyses will be based on the FAS by treatment group.

Anti-cancer treatment will be provided in a data listing with data retrieved from ‘Follow-up Cancer Therapy’, ‘Concomitant Radiation Therapy’, ‘Follow-up Radiation Therapy’, ‘Concomitant Surgery’, and ‘Follow-up Surgery’ eCRF pages.

Number and percentage of patients with any anti-cancer therapy after discontinuation will be tabulated overall and by type of therapy based on the data collected from the ‘Follow-up Cancer Therapy’, ‘Follow-up Radiation Therapy’ and ‘Follow-up Surgery’ eCRF pages.

## 6.6. Safety Summaries and Analyses

The Safety Analysis Set will be the primary population for safety evaluations. Summaries of AEs and other safety parameters will be based on the safety analysis set by treatment group.

### 6.6.1. Adverse events

Treatment-emergent adverse events (TEAEs) are those events with onset dates occurring during the on-treatment period for the first time, or if the worsening of an event is during the on-treatment period as defined in Section 3.5.1.

All analyses described below will be based on TEAEs (started during the on-treatment period) if not otherwise specified. The AE listings will include all AEs (whether treatment-emergent or not). AEs outside the on-treatment period will be flagged in the listings.

- **Related Adverse Events:** adverse events with relationship to study treatment (as recorded on the AE eCRF page, Relationship with study treatment = Related) reported by the investigator and those of unknown relationship (ie, no answer to the question ‘Relationship with study treatment’). Related AEs are those related to any study drug (ie, at least one of the study drugs).
- **Serious Adverse Events (SAE):** serious adverse events (as recorded on the AE eCRF page, Serious Adverse Event = Yes).
- **Adverse Events Leading to Dose Reduction:** adverse events leading to dose reduction of study treatment (as recorded on the AE eCRF page, Action taken with study treatment = Dose reduced).
- **Adverse Events Leading to Interruption of Study Treatment:** adverse events leading to interruption of study treatment (as recorded on the AE eCRF page, Action taken with study treatment = Drug interrupted). The eCRF does not allow for a clear separation between interruption of an infusion and delays of administration for a parenteral drug as both are recorded using the same term on the eCRF (“Drug interrupted”). IRRs will be excluded in the analysis of AEs leading to Drug Interruption in case they only led to an interruption of the infusion.

- **Adverse Events Leading to Permanent Treatment Discontinuation:** adverse events leading to permanent discontinuation of study treatment (as recorded on the AE eCRF page, Action taken with study treatment = Drug withdrawn).
- **Adverse Events Leading to Death:** adverse event leading to death (as recorded on the AE eCRF page, Outcome = Fatal, as well as AEs of Grade 5).
- **Immune-related Adverse Events (irAE):** irAEs (as identified according to the methodology outlined in Appendix 1 for a pre-specified search list of MedDRA PTs, documented in the Safety Review Plan and finalized for analysis of the current studies data prior to DB lock)
- **Infusion-related Reactions (IRR):** IRRs (as identified according to the methodology outlined in Appendix 2 for a pre-specified search list of MedDRA PTs documented in the Safety Review Plan and finalized for analysis of the current studies data prior to DB lock).

Unless otherwise specified, AEs will be summarized by number and percentage of patients with the AE in the category of interest as described above, by treatment group, primary SOC and PT in decreasing frequency for all patients.

Each patient will be counted only once within each SOC or PT. If a patient experiences more than one AE within a SOC or PT for the same summary period, only the AE with the strongest relationship or the worst severity, as appropriate, will be included in the summaries of relationship and severity.

